4.10.1 Disease Progression

Nivolumab and relatlimab are expected to trigger immune-mediated responses, which require activation of the immune system prior to the observation of clinical responses. Such immune activation may take weeks to months to be evident. Some subjects may have

objective volume increase of tumor lesions or other disease parameters within weeks following the start of immunotherapy. Such subjects may not have had sufficient time to develop the required immune activation or, in some subjects, tumor volume or other disease parameter increases may represent infiltration of lymphocytes into the original tumor. In conventional studies, such tumor volume or relevant laboratory parameter increases during the first 2-4 months of the study would constitute disease progression and lead to discontinuation of imaging to detect response, thus disregarding the potential for subsequent immune-mediated clinical response. This phenomenon was observed in approximately 10% of subjects in the Phase 1 study of nivolumab and has also been reported for ipilimumab monotherapy[38].

Subjects will be permitted to continue with treatment beyond RECIST 1.1 defined PD as long as they meet the following criteria:

- No symptoms or signs, including worsening of laboratory values, indicating disease progression*
- Investigator-assessed clinical benefit, and
- Subject is tolerating study drug.

The assessment of clinical benefit should take into account whether the subject is clinically deteriorating and unlikely to receive further benefit from continued treatment. The following criteria need to be taken into consideration:

- No decline in ECOG performance status.
- Absence of rapid progression of disease or of progressive tumor at critical anatomical sites (e.g., cord compression) requiring urgent alternative medical intervention.

All decisions to continue treatment beyond PD must be discussed with the IND Sponsor and documented in the study records.

Tumor assessments will be made using RECIST 1.1 and iRECIST (Appendix C and D).

4.10.2 Nivolumab- and Relatlimab-Related Adverse Events Requiring Permanent Discontinuation

Permanent discontinuation of all study treatment should be considered for any of the following:

- 1. Severe or life-threatening related AEs, including, but not limited to, any of the following (the IND Sponsor and BMS must be notified in the event of these AEs):
 - Any grade 2 treatment-related uveitis, eye pain, or blurred vision that does not respond to topical therapy and does not improve to ≤ Grade 1 severity within the re-treatment period OR requires systemic treatment

^{*}An exception to the above may be made for patients with PD who have only local symptoms that are amenable to radiation.

- Any grade 3 non-skin, drug-related AE lasting > 7 days or recurs, with the following exceptions:
 - Grade 3 treatment-related uveitis, pneumonitis, bronchospasm, neurologic toxicity, hypersensitivity reaction, or infusion reaction of any duration requires discontinuation
 - Grade 3 treatment-related endocrinopathies adequately controlled with only physiologic hormone replacement do not require discontinuation
 - Grade 3 treatment-related laboratory abnormalities do not require treatment discontinuation except:
 - o Grade 3 treatment-related thrombocytopenia > 7 days OR that is associated with bleeding requires discontinuation
 - Any treatment-related liver function test (LFT) abnormality that meets the following criteria require discontinuation:
 - ALT or AST > 8 x ULN, regardless of duration, or
 - ALT or AST > 5 x and \leq 8 x ULN, that fails to return to \leq Grade 1 within 2 weeks despite medical intervention, or
 - Total bilirubin $> 5 \times ULN$, or
 - Potential drug-induced liver injury (DILI) event (Section 6.5.5)
 - Elevated troponin ≥ Grade 3 requires discontinuation (except Grade 3 elevation without other signs of cardiac toxicity as determined by cardiac evaluation)
- Any grade 4 treatment-related AE or laboratory abnormality, except for the following events which do not require discontinuation:
 - Grade 4 neutropenia ≤ 7 days
 - Grade 4 lymphopenia and leukopenia.
 - Isolated Grade 4 amylase or lipase abnormalities that are not associated with symptoms or clinical manifestations.
 - Isolated grade 4 electrolyte imbalances/abnormalities that are not associated with clinical sequelae and are corrected with supplementation/appropriate management within 72 hours of their onset.
 - Grade 4 treatment-related endocrinopathy adverse events, such as adrenal insufficiency, ACTH deficiency, hyper- or hypothyroidism, or glucose

intolerance, which resolve or are adequately controlled with physiologic hormone replacement (corticosteroids, thyroid hormones) or glucose-controlling agents, respectively, may not require discontinuation after discussion with and approval from the IND Sponsor.

- Any dosing interruption lasting > 6 weeks with the following exceptions:
 - Dosing interruptions to allow for prolonged steroid tapers to manage drugrelated adverse events are allowed. Prior to re-initiating treatment in a subject with a dosing interruption lasting > 6 weeks, the IND Sponsor must be consulted. Tumor assessments should continue as per protocol even if dosing is interrupted. Periodic study visits to assess safety and laboratory studies should also continue every 6 weeks or more frequently if clinically indicated during such dosing delays.
 - Dosing interruptions > 6 weeks that occur for non-drug-related reasons may be allowed if approved by the IND Sponsor. Prior to re-initiating treatment in a subject with a dosing interruption lasting > 6 weeks, the IND Sponsor must be consulted. Tumor assessments should continue as per protocol even if dosing is interrupted. Periodic study visits to assess safety and laboratory studies should also continue every 6 weeks or more frequently if clinically indicated during such dosing delays.
- Any AE, laboratory abnormality, or intercurrent illness which, in the judgment
 of the Investigator, presents a substantial clinical risk to the subject with
 continued nivolumab or relatlimab dosing.

In order to standardize the management of AEs for all subjects, treatment management algorithms are included in **Appendix B**. Additional AE treatment management algorithms included in the nivolumab and relatlimab IB might be considered for individual cases.

4.11. End of Treatment (EOT)

All subjects will return to the study site 30 days (\pm 7 days) after the last dose of study drug (or within 7 days prior to initiation of a new anti-cancer treatment, whichever comes first) for an EOT evaluation. Procedures and assessments performed at this visit and beyond should follow the respective guidelines described in **Sections 4.12 and 9** as appropriate.

4.12. Duration of Follow Up

4.12.1 Safety Follow-up

Subjects who discontinue treatment should be contacted by telephone or email at 100 days (+ 14 day reporting window) from their last dose of study drug or within 7 days before initiation of a new antineoplastic treatment (whichever comes first) to assess for treatment

related toxicities. In addition, all SAEs occurring during this time should be reported as well.

Subjects who are discontinued from the study treatment due to an unacceptable drugrelated AE will be monitored for safety until the resolution of the AE to \leq grade 1 or stabilization or until initiation of a new therapy for their cancer, whichever occurs first.

4.12.2 Clinical Follow-up

All enrolled subjects who discontinue treatment without disease progression will enter the clinical follow-up portion of the trial. Subjects will begin the clinical follow-up period after they complete the EOT visit. Clinical follow-up visits will occur every 12 weeks (\pm 2 weeks) until: 1) start of a new antineoplastic therapy (information of the new cancer therapy will be collected), 2) disease progression, 3) death, 4) withdrawal of consent, or 5) study closure, whichever occurs first. Refer to **Section 9** for the schedule of assessments that should be performed at each visit. After disease progression or start of a new antineoplastic therapy, subjects will enter the survival follow-up portion of the trial (**Section 4.12.3**).

4.12.3 Survival Follow-up

Subjects who discontinue treatment and have disease progression will enter the survival follow-up portion of the trial. Subjects should be contacted every 12 weeks (\pm 2 weeks) to monitor overall survival. Information of other cancer therapies after discontinuation from the study treatment will be collected as well.

5. DOSING DELAYS/DOSE MODIFICATIONS

5.1. Dose Modifications

Subjects will be monitored continuously for AEs while on study drug. Subjects will be instructed to notify their physician immediately for any and all AEs. Dose escalations or reductions of nivolumab or relatlimab will not be allowed.

, patients who

enrolled prior to Amendment 7 and are within 8 weeks of their first dose will be dose reduced to 160mg or 480mg relatlimab at the discretion of the Principal Investigator. Patients who are past 8 weeks from their first dose may continue to receive relatlimab 960mg or be dose reduced to 160mg or 480mg at the discretion of the Principal Investigator.

5.2. Dose Delays

In some cases, the natural history of select AEs associated with immunotherapy can differ from and be more severe than AEs caused by other therapeutic classes. Early recognition and management may mitigate severe toxicity.

Guidance for Investigators is provided in the current relatlimab and nivolumab Investigator's Brochures. Additionally, management algorithms have been developed to assist Investigators with select toxicities and can be found in **Appendix B.** Toxicities for which management algorithms have been developed include:

- Pulmonary
- Gastrointestinal
- Hepatic
- Endocrine
- Dermatologic
- Neurologic
- Renal
- Myocarditis

Subjects who experience the following must have all study drugs held:

- Select drug-related AEs and drug-related laboratory abnormalities:
 - o Grade ≥ 1 pneumonitis
 - o Increase from baseline of ≥ one grade (to at least grade 2) of AST, ALT, and/or total bilirubin
 - \circ Grade ≥ 2 creatinine
 - \circ Grade \geq diarrhea or colitis
 - o Grade \geq 2 neurological AE
 - o Grade 4 amylase and/or lipase abnormalities regardless of symptoms or clinical manifestations
 - o Troponin >ULN requires a dose delay to allow for prompt cardiac evaluation
 - Between > 1 to $2 \times ULN$ will be permitted if a repeat assessment remains $\leq 2 \times ULN$ and patient undergoes a cardiac evaluation
- Any AE, laboratory abnormality, or intercurrent illness which, in the judgment of the investigator, warrants delaying the dose of study drug.

Subjects not meeting guidelines for permanent discontinuation will be permitted to resume therapy when the treatment-related AE(s) resolve to grade ≤ 1 or baseline value, with the following exceptions:

- If the toxicity resolves to ≤ Grade 1 or baseline > 6 weeks after last dose, but the subject does not otherwise meet criteria for permanent discontinuation, and the Investigator believes that the subject is deriving clinical benefit, then the subject may be eligible to resume the study drugs following the approval of the IND Sponsor.
- Subjects with grade 4 drug-related amylase and/or lipase increase that is not associated with symptoms or clinical manifestations of pancreatitis can be restarted on therapy once the levels have recovered to grade 3 or less.
- Subjects may resume treatment in the presence of Grade 2 fatigue.
- Subjects with baseline grade 1 AST, ALT or total bilirubin who require dose delays for reasons other than a drug-related hepatic event may resumed treatment in the presence of grade 2 AST, ALT or total bilirubin elevation.

- Subjects who require dose delays for drug-related elevations in AST, ALT, or total bilirubin may resume treatment when these values have returned to their baseline CTCAE grade or normal, provided the criteria for permanent discontinuation are not met.
- Treatment-related endocrinopathies adequately controlled with only physiologic hormone replacement may resume treatment.

Subjects eligible to resume study drug will resume study drug at the treatment visit following their last received study drug dose.

The on treatment tumor assessments (i.e., CT/MRI, positron emission tomography [PET], etc.) will continue on an every 8-week schedule relative to the subject's first dose regardless of any treatment delay incurred. Subjects who are required to permanently discontinue both study drugs are listed in **Section 4.10.**

6. ADVERSE EVENTS: LIST AND REPORTING REQUIREMENTS

This study will use the descriptions and grading scales found in the revised CTCAE version 5.0 for AE reporting.

Information about all AEs, whether volunteered by the subject, discovered by investigator questioning, or detected through physical examination, laboratory test or other means, will be collected, recorded, and followed as appropriate.

6.1. **Definitions**

6.1.1 Adverse Event

An AE is defined as any undesirable sign, symptom or medical condition occurring after starting the study drug (or therapy) even if the event is not considered to be related to the study. An undesirable medical condition can be symptoms (e.g., nausea, chest pain), signs (e.g., tachycardia, enlarged liver) or the abnormal results of an investigation (e.g., laboratory findings, electrocardiogram). Medical conditions/diseases present before starting the study treatment are only considered AEs if they worsen after starting the study treatment (any procedures specified in the protocol). New medical conditions / diseases occurring before starting the study treatment but after signing the informed consent form will not be recorded as AEs. Additionally, expected progression of the disease being studied will not be recorded as an adverse event.

Laboratory abnormalities: Laboratory abnormalities present at the screening visit will be recorded as pre-treatment signs and symptoms. After study treatment administration, all grade 3 and 4 clinical laboratory results that represent an increase in severity from baseline will be reported as AEs. A grade 1 or 2 clinical laboratory abnormality should be reported as an AE only if it is considered clinically significant by the investigator (induce clinical signs or symptoms or require corrective therapy), meets the definition of an SAE, or requires the participant to have study drug discontinued or interrupted. It is expected that

wherever possible, the clinical rather than laboratory term would be used by the reporting investigator (e.g., anemia versus low hemoglobin value).

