3. PATIENT SELECTION

3.1. Eligibility Criteria

- 3.1.1. Age ≥ 18 years.
- 3.1.2. ECOG performance status of 0-1 (Appendix A).
- 3.1.3. Patients with histologically proven metastatic or locally advanced microsatellite stable (MSS) colorectal adenocarcinoma.
- 3.1.4. Cohort A: Primary lesion has a composite PD-L1/Mucin (CPM) score $\geq 15\%$.
- 3.1.5. Cohort B: Primary lesion has a composite PD-L1/Mucin (CPM) score < 15%.
- 3.1.6. Cohort C: Prior surgical resection of primary tumor. Prospective biomarker evaluation not required.
- 3.1.7. Patients who have received at least one prior cancer chemotherapy regimen in the locally advanced/metastatic setting. Adjuvant therapy can only be counted if recurrence occurred within 6 months of completing systemic chemotherapy.

- Radiosensitizing doses of chemotherapy are not considered systemic chemotherapy. Patients should be considered for standard therapies.
- 3.1.8. Presence of at least one lesion with measurable disease as defined by 10 mm in longest diameter for a soft tissue lesions or 15 mm in short axis for a lymph node by RECIST 1.1.
- 3.1.9. Patients must have available archival tissue from the surgical resection of their primary tumor for CPM score determination.
- 3.1.10. Patient's acceptance to have a tumor biopsy of an accessible lesion at baseline and on treatment if the lesion can be biopsied with acceptable clinical risk (as judged by the investigator).
- 3.1.11. Life expectancy of greater than 3 months.
- 3.1.12. Patients must have normal organ and marrow function as defined below:

 $\begin{array}{lll} \text{-} & \text{Leukocytes} & & \geq 2,000/\text{mm}^3 \\ \text{-} & \text{Absolute neutrophil count} & & \geq 1,500/\text{mm}^3 \\ \text{-} & \text{Platelets} & & \geq 100,000/\text{mm}^3 \\ \text{-} & \text{Hemoglobin} & & \geq 8.5 \text{ g/dL} \end{array}$

- Total bilirubin $\leq 1.5 \text{ x ULN}$ except subjects with Gilbert's

Syndrome, who must have normal direct

bilirubin

- AST(SGOT) and ALT(SGPT) $\leq 3.0 \text{ x ULN}$ - Albumin $\geq 2.8 \text{ g/dl}$

- Lipase and amylase < 1.5 x ULN Subjects with values > 1.5

ULN may enroll if there are neither clinical nor radiographic signs of a pancreatitis.

- Creatinine $\leq 1.5 \text{ x ULN or creatinine clearance (CrCl)}$

≥ 40 mL/min (if using the Cockroft-Gault

formula below):

Female CrC1 = (140 - age in years) x weight in kg x 0.8572 x serum creatinine in mg/dL

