6.5. Reporting

6.5.1 Adverse Events (AEs) and Serious Adverse Events (SAEs)

All AEs (both expected and unexpected) occurring from the first dose of study drug will be captured on the appropriate study-specific case report forms (CRFs).

A non-serious adverse event is an AE not classified as serious. All non-serious AEs (not only those deemed to be treatment-related) should be collected continuously during the treatment period and for a minimum of 100 days (+14 day reporting window) following the last dose of study treatment or before initiation of a new antineoplastic treatment (whichever comes first). Non-serious AEs should be followed to resolution or stabilization, or reported as SAEs if they become serious. Follow-up is also required for non-serious AEs that cause interruption or discontinuation of study drug and for those present at the end of

study treatment as appropriate. Non-serious AEs are to be provided to BMS in aggregate via interim or final study reports as specified in the agreement or, if a regulatory requirement [e.g., IND US trial] as part of an annual reporting requirement.

Subjects who experience a grade 2 or higher nivolumab or relatlimab-related AE should be discussed with the IND Sponsor.

Report AEs to the IND Sponsor within 24 hours once identified as an unacceptable toxicity (defined in Section 4.7).

All SAEs (including deaths) occurring from the first dose of study drug, throughout the study, and 100 days (+14 day reporting window) after the last dose of study drug or before initiation of a new antineoplastic treatment (whichever comes first) must be reported. All SAEs that the investigator considers related to the study drug occurring after the follow-up periods must be reported.

SAEs will be reported promptly to the IND Sponsor, Regulatory Specialist, and BMS within 24 hours of recognition of the adverse event using the form found in **Appendix E**. If this falls on a weekend or holiday, an email notification is acceptable but must be followed by an SAE reporting form on the next business day.

SAE reports and any other relevant safety information are to be sent to:

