- 20: Tumor biopsies to be taken (if a subject's tumor is thought to be reasonably safe and easy to biopsy) at baseline (any time prior to the first dose after eligibility is met) and at Cycle 2 (4-6 cores per time point). The Cycle 2 biopsy has a ± 1 week window. Additional optional biopsies may be obtained later in the course of study treatment. Fine needle aspiration will not be acceptable. Detailed instructions for tissue collection, processing and shipment are provided in the Laboratory Manual.
- 21: Cycle 1 Day 1 evaluations do not need to be repeated if they were conducted within 3 days of the pre-study evaluations. Window of +7 days is for cycle 2 and beyond.
- 22: EOT visit will occur 30 (±7) days after the final dose (or within 7 days prior to initiation of a new anti-cancer treatment, whichever comes first). NOTE: CT scan assessment at EOT will occur 30 days (± 4 weeks) after the final dose. If the EOT visit occurs early, an assessment for AEs should be made by telephone or email on day 30 (±1) after last study dose.
- 23: Subjects who discontinue treatment should be contacted by telephone or email at 100 days (+ 14 day reporting window) from their last dose of study drug or within 7 days before initiation of a new antineoplastic treatment (whichever comes first) to assess for treatment related toxicities. In addition, all SAEs occurring during this time should be reported as well.
- 24: Subjects who discontinue treatment without disease progression (Section 4.12.2) will enter the clinical follow-up portion of the trial. Clinical follow-up visits will occur every 12 weeks (± 2 weeks) until progression. After disease progression, subjects will enter the survival follow-up portion of the trial.
- 25: Subjects who discontinue treatment and have disease progression (Section 4.12.3) will enter the survival follow-up portion of the trial. Subjects should be contacted every 12 weeks (± 2 weeks) to monitor overall survival. Information of other cancer therapies after discontinuation from the study treatment will be collected as well.
- 26: Research samples will be collected at the discretion of the PI based on availability of supplies and safety of patient and staff.

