- 20: Tumor biopsies to be taken (if a subject's tumor is thought to be reasonably safe and easy to biopsy) at baseline (any time prior to the first dose after eligibility is met) and at Cycle 2 (4-6 cores per time point). The Cycle 2 biopsy has a ± 1 week window. Additional optional biopsies may be obtained later in the course of study treatment. Fine needle aspiration will not be acceptable. Detailed instructions for tissue collection, processing and shipment are provided in the Laboratory Manual.
- 21: Cycle 1 Day 1 evaluations do not need to be repeated if they were conducted within 3 days of the prestudy evaluations. Window of +7 days is for cycle 2 and beyond.
- 22: EOT visit will occur 30 (±7) days after the final dose (or within 7 days prior to initiation of a new anticancer treatment, whichever comes first). NOTE: CT scan assessment at EOT will occur 30 days (± 4 weeks) after the final dose. If the EOT visit occurs early, an assessment for AEs should be made by telephone or email on day 30 (±1) after last study dose.
- 23: Subjects who discontinue treatment should be contacted by telephone or email at 100 days (+ 14 day reporting window) from their last dose of study drug or within 7 days before initiation of a new antineoplastic treatment (whichever comes first) to assess for treatment related toxicities. In addition, all SAEs occurring during this time should be reported as well.
- 24: Subjects who discontinue treatment without disease progression (**Section 4.12.2**) will enter the clinical follow-up portion of the trial. Clinical follow-up visits will occur every 12 weeks (± 2 weeks) until progression. After disease progression, subjects will enter the survival follow-up portion of the trial.
- 25: Subjects who discontinue treatment and have disease progression (Section 4.12.3) will enter the survival follow-up portion of the trial. Subjects should be contacted every 12 weeks (± 2 weeks) to monitor overall survival. Information of other cancer therapies after discontinuation from the study treatment will be collected as well.
- 26: Research samples will be collected at the discretion of the PI based on availability of supplies and safety of patient and staff.
- 27: If nivolumab and relatlimab are being administered sequentially (due to Relatlimab 480 or 960mg dose), the order of administration is nivolumab followed by relatlimab. Subjects should be observed for a minimum of 30 minutes between each infusion.

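### AE and SAE collection starts at the first dose, so the protocol does not require complications of the pre-dose research biopsy to be captured on AE/SAE forms or reported

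*Combined protocol and SAP*

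**What the plan says.** **Start of the AE window.** Section 6.1.1: "An AE is defined as any undesirable sign, symptom or medical condition occurring after starting the study drug (or therapy"). The same section adds that new conditions "occurring before starting the study treatment but after signing the informed consent form will not be recorded as AEs". A condition already present before treatment counts only if it worsens afterwards.

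**Start of reporting.** Section 6.5.1: "All AEs (both expected and unexpected) occurring from the first dose of study drug will be captured" on the CRFs, and SAEs, deaths included, are reportable when "occurring from the first dose of study drug, throughout the study, and 100 days" after the last dose (with a 14-day reporting window, or until a new antineoplastic treatment if sooner). In both calendars (Sections 9.1 and 9.2) the adverse-event row has no mark under screening.

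**The pre-dose procedure.** Footnote 20 of both calendars schedules tumor biopsies "at baseline (any time prior to the first dose after eligibility is met) and at Cycle 2 (4-6 cores per time point"), if the tumor is judged reasonably safe and easy to biopsy. The biopsy row also carries footnote 26: "Research samples will be collected at the discretion of the PI based on availability of supplies and safety of patient and staff". Section 3.1 makes it an inclusion criterion: "Patient's acceptance to have a tumor biopsy of an accessible lesion at baseline and on treatment", subject to acceptable clinical risk. Section 8.1 lets tissue from a biopsy in the 28 days before first dose serve as the baseline sample.

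**Attribution.** Section 6.2 assesses relationship to study drug only. The SAE form in Appendix E offers nivolumab, relatlimab and underlying disease.

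**The concern.** A core biopsy done for correlative research carries a risk that the patient runs because of the trial. Ordinarily a trial records harm from procedures it adds, whether or not the drug has been given. Here the collection window opens after the first such procedure, and by an express rule rather than by omission.

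Three things are at stake. A serious complication such as a bleed or a hospitalization, if it occurs before dosing, triggers no mandatory AE or SAE entry. If it persists, it becomes a pre-existing condition, which is an AE only if it worsens. If the patient is never dosed, that patient is also outside the safety analysis, which Section 12.2 restricts to treated subjects. The point concerns oversight of procedural risk; it does not touch the response-rate analysis.

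**Working it through.** The plan states no figure on this point, so there is nothing to reproduce. The check is mainly a comparison of sections, followed by an illustration of size.

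**Step 1: follow one event through the rules.** Take the same biopsy complication at each of the two scheduled time points.

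| Question | Baseline biopsy | Cycle 2 biopsy |
|---|---|---|
| Timing (footnote 20) | Before first dose | After first dose |
| Is it an AE under 6.1.1? | No, a new condition between consent and treatment is excluded | Yes, related to drug or not |
| CRF capture under 6.5.1? | Not required | Required |
| SAE report to IND Sponsor and BMS if serious? | Not required | Required |
| In the 12.2 safety analysis? | No | Yes |
| Attribution to the procedure (6.2, Appendix E)? | No category | No category |

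The two time points differ in whether the event is captured. Neither offers a way to attribute it to the procedure.

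**Step 2: look for another rule that closes the gap.**
- Section 4.10 has the reason and date of study removal entered in the CRF.
- Section 6.5.7 sends deaths to the IRB whatever the cause, but lists them as a class of SAE; otherwise it refers to institutional guidelines.
- Section 11.2 puts participant safety on the agenda of weekly meetings.
- Section 11.3 assigns oversight to a safety monitoring committee under an institutional plan that is not in the documents.

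Each could bring an event to light. None requires a non-fatal pre-dose complication to be recorded as an AE or reported as an SAE.

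**Step 3: size, as an illustration.** Inputs: 32 evaluable patients per cohort and 18 in stage 1 (Sections 1.4 and 12.1), three cohorts. Full enrollment: n = 3 × 32 = 96. Every cohort stopping at stage 1: n = 3 × 18 = 54. The serious-complication rate p per biopsy is assumed. Expected events = n × p; chance of at least one = 1 − (1 − p)^n.

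| Assumed p | n = 54: expected | n = 54: at least one | n = 96: expected | n = 96: at least one |
|---|---|---|---|---|
| 0.5% | 0.27 | 24% | 0.48 | 38% |
| 1% | 0.54 | 42% | 0.96 | 62% |
| 3% | 1.62 | 81% | 2.88 | 95% |

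Every cell assumes a new baseline biopsy in each evaluable patient. Reused tissue, unsafe lesions and investigator discretion all lower the count. Patients biopsied and then replaced before dosing (Section 10.1) would add to it. The documents size none of these, but because footnote 20 puts the biopsy after eligibility is met, the never-dosed group is probably small.

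**The case against.** The best defense is that a first-dose start is a deliberate choice suited to a drug-safety endpoint: the secondary endpoint in Section 10.2 concerns drug toxicity, and pre-dose events would only dilute it. That is right for the analysis, and the analysis should stay as it is. It does not explain why harm from a procedure the trial adds should need no record at all.

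A reader might infer more than the documents support:
- **That the harm would be invisible to those overseeing safety.** Not shown. Weekly meetings cover participant safety without limiting it to dosed patients, and the committee's remit sits in an institutional plan not available here.
- **That patients harmed and never dosed vanish from the record.** Not shown. Section 4.10 requires the reason for removal in the CRF, and Section 10.1 provides for subjects who leave before the first dose. They leave the analyses, not necessarily the record.
- **That one to three serious events will go unrecorded.** That takes 96 biopsies and a 1-3% rate as given. The count is a ceiling and the rate is an assumption.
- **That Section 6.1.1 flatly contradicts Section 6.5.1.** Section 6.1.1 has a parenthesis mentioning protocol-specified procedures, attached to the sentence on worsening of earlier conditions. It may extend the meaning of study treatment or may be a stray fragment. The sentence that follows it and Section 6.5.1 both point to the first dose, so it is an ambiguity to clarify.

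What survives the defense is the absence of a required capture and reporting route.

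**Conclusion.** The point holds in limited form. As written, the protocol does not require complications of the pre-dose research biopsy to be captured on AE/SAE forms or reported to the IND Sponsor and BMS, while it does require this for the Cycle 2 biopsy. This follows from the text and depends on no assumed rate.

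The size is an upper bound: at an assumed serious rate of 0.5-3%, about 0.3 expected events (54 biopsies, 0.5%) to 2.9 (96 biopsies, 3%), lower with reuse or unsafe lesions. The primary response rate, the sample size and the all-treated safety analysis are unaffected. It is worth correcting because the gap bears on patient safety and is cheap to close.

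**What to change.** - **Sections 6.1.1 and 6.5.1:** record AEs and report SAEs judged related to a protocol-specified procedure from consent, or from the first study-specific procedure, until the first dose. Reword or delete the parenthesis on procedures in 6.1.1 so that only one reading remains.
- **Section 6.2 and Appendix E:** add a procedure-relatedness category. Without it, the events collected could not be attributed, and this also applies to the Cycle 2 biopsy.
- **Reporting:** list these pre-dose events separately, including for patients never dosed. Leave the all-treated analysis in Section 12.2 unchanged.

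The cost is a few extra CRF entries, an added field on the SAE form and an occasional SAE report before dosing.
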